#### **4.7.4.3 CD4 Lymphocyte Count**

Cluster of Differentiation 4 (CD4) lymphocyte count will also be tested for known HIV-positive subjects using a blood sample taken at Screening if a result is not available in the subject’s medical record or the result available is older than 1 year. Results will be listed only.

#### **4.7.4.4 Virology**

Retention samples for virology will be obtained at Screening and at the End-of-Study Visit. Results will be listed only.

#### 4.7.5 Vital Signs

Vital signs including blood pressure, heart rate, temperature, and respiratory rate will be documented:

- For PTPs during the screening period, every 3 months until the subject reached 50 EDs and then yearly until End of Study visit.
- For PUPs during the screening period, before and at 1, 2, 3, and 6 hours after the first rVIII-SingleChain injection, every 3 months until the subject reached 50 EDs, then yearly until End of Study visit. For PUPs enrolled into the CCI [REDACTED] vital signs will be collected also during enrolment into the CCI [REDACTED], at the following monthly visits and at the end of the CCI [REDACTED].

- CCI [REDACTED]

Vital sign results along with the change from baseline will be summarized by scheduled visit.

CCI [REDACTED]

Vital signs results will be summarized for the Safety population and will be presented by PUPs and PTPs separately and by age subgroups based on age in this study: for PTPs: 0 to < 6 years, ≥ 6 to < 12 years, ≥ 12 to < 18 years and ≥ 18 to ≤ 65 years, 0 to <12 years, ≥12 to ≤ 65 years.

#### 4.7.6 Physical Examination

A physical examination will be conducted by the investigator or delegate according to the schedule of events as in the CSP. A standard of care physical examination for each subject will be performed. Any unfavorable findings considered by the investigator as clinically significant at any point in the study will be documented in the eCRF as an AE.

At Screening clinically significant abnormal findings are to be reported on the Medical/Surgical History form. For all other visits, new clinically significant abnormal findings or clinically significant deteriorations are to be reported on the Adverse Events form. Results will be listed in the corresponding listing.

#### 4.7.7 Incremental Recovery

Incremental recovery (IR) will be calculated with and without adjustment for any baseline endogenous predose FVIII activity levels. Baseline-uncorrected analysis will be done with the unchanged concentration FVIII activity level profiles, while baseline-corrected analysis will be done with transformed values (baseline or pre-dose activity levels subtracted from all the post-infusion measurements).

Only central laboratory FVIII concentration/activity levels quantified using validated chromogenic substrate assay (ChS) will be used in the analysis. IR will be derived using the concentrations FVIII activity levels obtained from the ChS assay.

IR is defined as FVIII activity obtained 30 minutes after injection, divided by the dose of rVIII-SingleChain (IU/dL / IU/kg). The exact time of blood draw after infusion will be recorded and used in the analysis (if needed). All values below the limit of quantification will be treated as zero (0) values.

Descriptive statistics (n, mean, standard deviation [SD], coefficient of variation [CV], median, minimum, and maximum, along with geometric mean, and 95% CIs around the geometric mean) will be presented for IR.

Individual FVIII activity levels will be presented to the significant digits available in the source data and IR will be formatted to 3 significant digits. Parameters or statistics which cannot be determined will be represented in the tables by “-“ for not applicable.

FVIII measured before dose and after dose at Day 1, ED 10, ED 50 and ED 100 will be summarized by age group for PTPs (0 to < 6 years,  $\geq 6$  to < 12 years,  $\geq 12$  to < 18 years and  $\geq 18$  to  $\leq 65$  years, 0 to <12 years,  $\geq 12$  to  $\leq 65$  years)

IR will be also summarized in the following Total ED ranges based on first dose in the pivotal study (PTPs) or on first dose in this study (PUPs): 0-10 EDs, >10-15 EDs, >15-50 EDs, >50-75 EDs, >75-100 EDs, >100. For PUPs only the ranges 0-10 EDs, >10-25 EDs, >25-50, and > 50 EDs will be reported. If more than one assessment is included in the same EDs range, then the most recent one will be considered. Definition of assessments at EDs=0 and handling of assessments done on the same date and time of a dose will be as detailed in [Section 4.7.1](#).

Analysis will be repeated considering EDs achieved in the current study only.

IR will be also summarized by reason for specimen collection. If more than one assessment has the same reason, then the most recent one will be considered.

For PUPs, results will be presented overall and by inhibitor status at time of the assessment.

CCI

## 4.8 Adjustment for Covariates

Not applicable.

### 4.8.1 Center Effects

There are no plans to display results by center.

## 4.9 Protocol Deviations

Deviations from the protocol will be documented on an ongoing basis throughout the study period. All protocol deviations will be summarized and listed with type and details of deviation.

## 4.10 Deviations from SAP

Any deviations from the original statistical plan will be described and justified in the final clinical study report,.

## 4.11 Changes in Conduct or Planned Analyses from the Protocol

Section 2.1 and 2.2: In the protocol, incidence of inhibitor formation to FVIII in Arm 2, PUPs is stated that would be performed on at least 50 PUPs. However, this condition has been removed. Given that patients that develop inhibitors may be withdrawn from the study early, they would not necessarily achieve 50 exposure days but we would definitely have to include them in the calculation. Therefore the text was adjusted to ensure the option to properly report the endpoint regardless of these circumstances.

CCI

Section 3.5.3: Efficacy Population definition has been changed removing the exclusive inclusion of subjects who do not have an inhibitor at any time point during the study.

CCI

Section 4.6.1 and 4.6.2.1: In the Annualized Bleeding Rate analysis it has been added that subjects with an efficacy evaluation period less than 8 weeks (56 days) will be excluded from the analysis to exclude bias due to short evaluation period.

Section 4.6.2.2: The analysis of number of infusions of CSL627 required to achieve hemostasis has been added for completeness of analysis.

Section 4.7.1: Incidence of transient inhibitors has been added for completeness of analysis.

Section 4.7.2.1: Analysis of AESIs has been added for completeness of analysis.

## 4.12 Missing Values

### 4.12.1 Handling Partial Dates

A date is a valid partial date if the day is missing, or the day and the month are missing. Where appropriate, the algorithm outlined in [Table 2](#) will be applied to accommodate partial dates.

**Table 2: Handling Partial Dates**

Date	Missing Element(s)	Imputation
Start date	Day and Month	First day of the year
	Day	First day of the month
Stop date	Day and Month	Last day of the year
	Day	Last day of the month

### 4.12.2 Early Withdrawal or Missing data

Refer to the handling of partial dates in [Section 4.12.1](#) and method of analysis for the primary efficacy endpoint in [Section 4.6.1.1](#). Other than these two items, no imputation due to withdrawals or missing data will be applied.

## 4.13 Algorithms/SAS Codes

- **Tables that need descriptive statistics – continuous variables:**

```
PROC UNIVARIATE DATA=dset NOPRINT;
  VAR var1 var2 var3 ...varn;
  BY byvar; (optional)
  OUTPUT OUT=outname
  N=n MEAN=mean MIN=min MAX=max MEDIAN=median STD=std Q1=q1 Q3=q3;
RUN;
```

- **Tables that need frequency counts:**

```
PROC FREQ DATA=dset NOPRINT;
  BY byvar; (optional)
  TABLES var1 *var2;
  OUTPUT OUT=outname;
RUN;
```

- **Tables that need 95% CIs within group for binomial proportions:**

```
PROC FREQ DATA=dset;
  BY byvar; (optional)
```

```
TABLES var1;  
EXACT BINOMIAL; RUN;
```

- **Tables that require generalized linear modelling, including 95% CIs:**

```
PROC GENMOD DATA= dset;  
  CLASS subject;  
  MODEL 'bleeding events / time on csf = < treatment>' /CL DIST=POISSON  
offset=logtime link=log;  
  LSMEANS < treatment> /diff=control exp cl;  
  WHERE wherever; (optional)  
RUN;
```

- **The geometric mean is the antilog of the arithmetic mean of the logs:**

```
DATA dset;  
  SET dset old;  
  LOGx = LOG(x);  
RUN;  
  
PROC UNIVARIATE DATA=dset NOPRINT;  
  VAR LOGx;  
  OUTPUT OUT=outname  
  MEAN=logmean;  
RUN;  
  
DATA outname;  
  SET outname;  
  geomean = EXP(logmean);  
RUN;
```

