11.3.2.1 Primary Efficacy Analysis

For **Arms 1 and 3 (PTPs)**, there is no primary efficacy endpoint.

For **Arm 2 (PUPs)**, the analyses of the primary efficacy endpoints are outlined below:

- The investigator's clinical assessment of hemostatic efficacy for the treatment of **major** bleeding episodes, based on the 4-point ordinal scale (excellent, good, moderate, poor / no response), will be tabulated. The percentage of major bleeding episodes treated successfully (defined as ratings of excellent or good) will be summarized, and reported together with a two-sided 95% CI. To estimate the proportion, the denominator will include all treated bleeding episodes categorized as major. To account for within-subject correlation, generalized linear modeling using SAS' GENMOD procedure will be utilized. The model will contain only the intercept term. The binomial distribution with logit link function will be specified.
- The AsBR will be derived for each subject as follows: ((number of spontaneous bleeding episodes) / (observed treatment period of interest))*365.25. The AsBR will be summarized by regimen (on-demand or prophylaxis) using descriptive statistics. In addition, the number of spontaneous bleeding episodes per year and associated 95% CI will be estimated based on a Poisson model. Generalized linear modeling using SAS' GENMOD procedure will be utilized. The Poisson distribution with log link function, and log_time offset will be specified. The Poisson-based number of spontaneous bleeding episodes per year will be presented by regimen (on-demand or prophylaxis).

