### AsBR

AsBR will be derived by inhibitor status and overall as follows:

$$(\text{number of bleeding events}) / (\text{observed treatment period of interest days}) * 365.25.$$

Only bleeding events requiring treatment will be included in the derivation of bleeding rates. The AsBR will be estimated for subjects who complete at least 8 weeks of treatment on the given inhibitor status using the subject's observed data. If the subject does not complete at least 8 weeks of treatment on the given inhibitor status, then the AsBR will be considered missing.

The number of spontaneous bleeding episodes per year based on a Poisson model and associated 95% CI and the number and percentage of subjects with zero bleeding episodes will be presented. In addition, the rate ratio of Prophylaxis modality to On-Demand modality (Prophylaxis- On-Demand) will be presented, along with the associated 95% CI, as obtained by the Poisson model.

Spontaneous bleeding episodes are those classified as 'Non-traumatic' in e-Diary or 'Spontaneous' in the eCRF. Annualized spontaneous bleeding rate will also be summarized for the following subgroup:

- Positive non-inhibitory Anti-Drug Antibodies (ADAs) and negative during the study
- Age based on age in this study: for PTPs: 0 to < 6 years,  $\geq 6$  to < 12 years,  $\geq 12$  to < 18 years and  $\geq 18$  to  $\leq 65$  years, 0 to <12 years,  $\geq 12$  to  $\leq 65$  years.
- Prophylaxis frequency: every second day, 3 times per week, 2 times per week, other regimen.

In these subgroup analyses rate ratio of Prophylaxis modality to On-Demand modality won't be displayed.

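### The SAP's Poisson template divides bleeds by time in the response and also offsets log time; if programmed as a rate response, the model-based yearly rate, the rate ratio and their CIs would be wrong

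*SAP*

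**What the plan says.** Protocol 11.3.2.1 defines two outputs for the AsBR, a primary endpoint in PUPs. The first is a per-subject value, "number of spontaneous bleeding episodes) / (observed treatment period of interest))*365.25", summarised descriptively by regimen. The second is a model-based number of spontaneous bleeds per year with a 95% CI: "The Poisson distribution with log link function, and log_time offset will be specified". Protocol 11.3.2.2 repeats the same analyses for the ABR in all arms.

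The AsBR part of SAP 4.6.1.1 keeps both outputs. It asks for "The number of spontaneous bleeding episodes per year based on a Poisson model and associated 95% CI" and adds a comparison: "the rate ratio of Prophylaxis modality to On-Demand modality (Prophylaxis- On-Demand) will be presented". It counts only bleeds that needed treatment. It names neither the response variable nor an offset.

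The only model code in the SAP is the template in 4.13. Its lines include "CLASS subject", then "MODEL 'bleeding events / time on csf = < treatment>' /CL DIST=POISSON", continued by "offset=logtime link=log", then "LSMEANS < treatment> /diff=control exp cl".

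**The concern.** In a Poisson model with a log link, the log-time offset is what turns a count into a rate. If the response has already been divided by time, the offset divides by time again. The template shows both, so read as arithmetic it contradicts the protocol's model. Because SAP 4.6.1.1 says only that a Poisson model is used, the template is the SAP's sole statement of how that model is built.

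At stake are the model-based yearly rate for a primary endpoint, the only between-regimen comparison of it, and both intervals. The ratio is exposed because follow-up is tied to exposure. Inhibitor-negative PUPs stay until 75 EDs (Protocol 3.3), so a boy injected on a schedule can finish much sooner than one injected mainly when he bleeds.

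**Working it through.** The documents state no bleeding rate, ratio or follow-up by regimen, so there is no figure of the plan's own to reproduce. The check is algebra followed by worked examples. Every rate and follow-up time below is an assumption unless a source is named.

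**1. Intercept-only model.** For subject i with y bleeds in time t:
- count response with offset log(t): exp(b) = Σy / Σt
- response y/t with offset log(t): exp(b) = Σ(y/t) / Σt

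**2. Seven-subject example.** t = 0.5, 0.6, 0.7, 1, 2, 3, 3.5 years; y = 1, 1, 1, 2, 4, 6, 7.
- Σy = 22, Σt = 11.3, Σ(y/t) = 2 + 1.667 + 1.429 + 2 + 2 + 2 + 2 = 13.095
- count with offset: 22/11.3 = 1.947 per year (95% CI 1.28 to 2.96)
- rate with offset: 13.095/11.3 = 1.159 (0.67 to 1.99), which is 40% lower
- the same error with time in days, rescaled by 365.25: 1.159/365.25 = 0.003 per year

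**3. Rate ratio.** If the rate is constant within a regimen, the doubly adjusted estimate is that rate divided by mean follow-up. Hence:

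ratio obtained = true ratio × (mean follow-up on-demand / mean follow-up prophylaxis)

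For a true ratio of 0.25 and follow-up of 0.6 years (prophylaxis) and 1.5 years (on-demand): 0.25 × 2.5 = 0.63. With 0.6 and 3.0 years: 0.25 × 5 = 1.25.

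**4. Plausible prophylaxis follow-up.** SAP 3.2.1 reports 2 to 3 injections per week among the usual schedules in previous studies. At that frequency 75 EDs take 75/3 = 25 to 75/2 = 37.5 weeks, or 0.48 to 0.72 years. Protocol 3.3 expects a study duration of up to 6 years, without splitting it by regimen.

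**5. Fitted examples.** Assumed 12 subjects per regimen, 2 bleeds per year on prophylaxis and 20 on-demand, true ratio 0.10, time in years:

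| Follow-up, prophylaxis / on-demand | Count + offset: ratio (95% CI) | Rate + offset: on-demand; prophylaxis per year | Rate + offset: ratio (95% CI) |
|---|---|---|---|
| 0.72 / 2 | 0.100 (0.062–0.162) | 10; 2.78 | 0.278 (0.183–0.423) |
| 0.72 / 5 | 0.100 (0.062–0.161) | 4; 2.78 | 0.696 (0.457–1.058) |
| 2 / 1 | 0.100 (0.073–0.136) | 20; 1 | 0.050 (0.033–0.076) |
| 2 / 2 | 0.100 (0.074–0.135) | 10; 1 | 0.100 (0.066–0.152) |
| 1 / 1 | 0.100 (0.066–0.152) | 20; 2 | 0.100 (0.066–0.152) |

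The yearly rate is too low when mean follow-up exceeds one year and too high when it is shorter. With equal follow-up the ratio's point estimate survives, but its CI is right only if everyone is followed for exactly one time unit. With time in days the first row keeps the ratio 0.278, but its interval runs from 0.00009 to 846.

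**6. Simulation.** 2,000 runs; 18 prophylaxis subjects followed 0.5 to 1 year and 6 on-demand subjects followed 1 to 4 years; true rates 2 and 8, true ratio 0.25. Count with offset: median ratio 0.248, CI coverage 95.7%. Rate with offset: median ratio 0.817, coverage 1.0%.

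**The case against.** The strongest reply is that the SAP does not actually prescribe a double division. The MODEL content is in quotation marks, with angle-bracket placeholders and an undefined time variable. A slash in the response is GENMOD's events/trials form for binomial data. The line has to be rewritten before it runs. It can be read as describing the rate being modelled, with the offset as the means of modelling it; on that reading time is divided out once. A programmer who works from the protocol text gets the right model. All of this stands. It means the error is conditional on how the template is turned into code. It does not remove the conflict, because the SAP text names no response variable and the one place that does shows a rate.

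A reader might also infer that the AsBR itself and every ABR are wrong. The documents do not support that. The per-subject values divide the count by the period once, and their descriptive summaries are part of the primary output.

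Finally, the size is built on assumptions. The PUP schedule is at the investigator's discretion, regimens may be switched, inhibitor-positive PUPs may stay up to 3 years longer, and the 6-year duration is not specific to on-demand treatment. That also stands.

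**Conclusion.** The point holds as a defect in the specification. The SAP's only template for the bleeding-rate model conflicts with the protocol's model, and one natural way of making it run gives wrong yearly rates, a wrong ratio and wrong CIs. The form of the error follows from the algebra. The simple factor for the ratio also needs a roughly constant rate within each regimen. Its size depends on follow-up times that the documents do not give: in the examples a true ratio of 0.10 came out anywhere from 0.050 to 0.696.

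Three stronger readings are tempting and not supported. The final analysis is not shown to be wrong, since the protocol text leads to the correct model. A reversed comparison is not established: the 1.25 in step 3 needs an assumed fivefold difference in follow-up. And the error is not always an understatement, as the 0.72-year rows show.

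The change is worth making before the PUP analysis because it costs almost nothing and protects the model-based estimate of a primary endpoint.

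**What to change.** Replace the Poisson template in SAP 4.13 with:

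- `CLASS subject regimen;`
- `MODEL bleeds = regimen / DIST=POISSON LINK=LOG OFFSET=logtime;`
- an LSMEANS statement for regimen that names on-demand as the control level, with exponentiated estimates and CIs.

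Define bleeds as the count of treated spontaneous bleeds (for the ABR, the relevant bleed type), and logtime as log(days in period/365.25), so that the exponentiated mean is a rate per year. Regimen must be in CLASS because LSMEANS uses it; the present template lists only subject. State the response and offset in SAP 4.6.1.1 as well.

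Do not repair the template by keeping the rate and dropping the offset: that averages subject rates without weighting by follow-up and gives wrong CIs.

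Add one programming check: an intercept-only fit must equal total bleeds divided by total years. SAP 4.1.2 records the PTP analysis as completed, so for any Poisson ABR results there, apply the same check to the program that was run.

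The cost is a few lines of SAP text and code and one check. No data collection changes.

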## 5 Tables and Listings

### 5.1 Format

The following conventions will be adopted for the outputs. These conventions will enhance the review process and help to standardize presentations.

- All tables, figures, and listings (where appropriate) will be presented in Landscape Orientation. A 9-point font size using the *Courier New* font is proposed.
- Legends will be used for all figures with more than 1 variable or item displayed.
- Only standard keyboard characters will be used in tables and figures. Special characters, such as non-printable control characters, printer specific or font specific characters, will not be used on a table or figure.
- All footnotes will be left justified and at the bottom of a page. Footnotes must be present on the page where they are first referenced. Footnotes will be used sparingly and only to add value to the table or figure. If more than four footnotes are planned then a cover page may be used to display the footnotes.
- All laboratory data will be presented in the Standard Units.
- All date values will be presented as DDMMYYYY (e.g., 08SEP2008) format.
- All observed time values will be presented using a 24-hour clock HH:MM:SS format (e.g., 13:35:56 or 14:22). Seconds will only be reported if measured.
- Time durations will be reported in mixed HHh MMm SSs notation (e.g., 5h 32m, or 27h 52m 20s). Decimal notations will not be used to present time durations.
- All tables and figures will have the name of the program and a date/time stamp on the bottom of each output.
- Populations represented on the tables or figures will be clearly identified in the last title of the Table.
- Consistent terminology will be used to define and identify a population.
- Population sizes will be presented for as totals in the column heading as (N=xxx), where appropriate.
- All study population and baseline characteristics and safety summaries will include a Total column where appropriate.
- All population summaries for continuous variables will include n, mean, SD, median, minimum, and maximum. Other descriptive statistics (e.g., quartiles, coefficient of variation) may be reported when appropriate.
- The minimum and maximum values will be presented with the same number of decimal places as the raw data collected. The mean and percentiles (e.g. median, Q1, and Q3) will be presented using one additional decimal place. The standard deviation and standard error will be presented using two additional decimal places. PK parameters should have a minimum of 3 significant figures.
- Percentages will be presented to 1 significant decimal place in general. The denominator will be the total size of the sample, N, unless otherwise noted.

- Any p-values reported on default output from statistical software may be reported at the default level of precision, with one exception: p-values of 0.0000 or 10E-4 or below will be reported as <0.0001.
- The *left and right margins* of all tables and listings will be a minimum of 2.1 cm from the left and 1.9cm from the right. The *top and bottom margins* will be a minimum 2.92cm. *Header and footer* will be both 1.27 cm.

## 5.2 Tables

The list of tables and associated shells are provided in a separate document.

## 5.3 Figures

The list of figures and associated shells are provided in a separate document.

## 5.4 Listings

The list of listings and associated shells are provided in a separate document.

## 5.5 Appendices

NA

